Subjects/Procedures: Subjects will be the same prodromal PD cohort described above in Aim 1. Subjects will continue the exercise intervention (or no intervention) for a total of 52 weeks to examine a potential disease-modifying effect. Subjects will continue to receive weekly phone calls from staff to monitor safety and compliance. At the end of the intervention period, control and exercise subjects will undergo repeat DaT SPECT with quantitation of signal in 6 different striatal regions (right and left caudate, right and left anterior putamen, right and left posterior putamen) and repeat exercise testing. If subjects choose to drop out, we will attempt to obtain the final DaT imaging study as soon as possible after notification of the subject's intent to withdraw if they have completed at least 24 weeks of the intervention.

AIM 3: To characterize the mechanism and biochemical correlates of exercise-induced changes in subjects with prodromal PD. In this aim, we will test the hypothesis that serum biomarkers of exercise effects and PD risk will change in the intervention group compared to no intervention.

Subjects/Procedures: Serum biomarkers associated with PD risk or exercise-induced changes (i.e. BDNF, uric acid and apolipoproteinA1) will be measured at baseline, 8 and 52 weeks as described above. The primary outcome of this aim will be differences in the rate of change between intervention groups as assessed using independent samples t-tests. A secondary outcome will examine the rate of change using linear mixed-effects models controlling for age, gender and other potential confounders. Additionally, relationships of biomarkers to VO2max, UPDRS, quantitative motor and quantitative DaT will be examined using partial correlations controlling for age and gender. An intention-to-treat analysis will be applied primarily but pre-planned secondary analyses will compare only exercise subjects deemed compliant with controls.

A schematic demonstrating the flow of recruitment, assessments and analysis is provided below:

[figure not shown]

Figure 3: Overview of study design

5.1.2. What research methods will be used in the project? *Check all that apply.*

 Surveys/Questionnaires	 Interviews	 Audio Taping
 Behavioral Observations	 Chart Reviews	 Video Taping

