Aim 2: Because DaT SPECT signal loss is most sensitively detected in the putamen (particularly posterior putamen) in early PD, we will use this region to power our analysis. In our analysis of longitudinal DaT SPECT data from the PPMI study, average putamen signal was 0.83 (0.30) at baseline and 0.68 (0.23) at year 1 (absolute change 0.15 (0.13)), representing the expected change in the non-intervention group. With 35 subjects per group expected to complete the study (accounting for 20% drop-out), we are able to detect at least 0.06 points difference of change in average putamen signal between intervention and control groups (i.e., control group changes by 0.15 and intervention group changes by 0.09) with 80% power using two-sample t-test (alpha=0.05). As described in our preliminary data, the rate of rate of striatal degeneration during the prodromal period that we will capture may be greater than what been reported for the clinically manifest period of PD. Thus, the above estimates of the required sample size are conservative and it is likely that we could detect a significant effect of the intervention even if fewer than projected subjects complete the intervention (owing to greater attrition or decreased recruitment). For example if the non-intervention change in DaT uptake is 10% higher than we assumed (0.165 vs. 0.15), we could detect a similar effect size of the intervention with 29 (rather than 35) subjects per group. If the rate were 20% higher, we could detect a similar effect with 24 subjects. If the baseline rate of decline were 0.2 rather than 0.15 (33% higher), we could detect the effect with only 20 subjects per group.

Aim 3: One study has measured BDNF levels in PD patients before and after an 8 week exercise intervention(28). Baseline levels were mean (SD) 21 (3.4) and average post-intervention levels were 25(6.4) in the intervention group with no significant change in the non-intervention group. With 35 subjects per group expected to complete the study (accounting for 20% drop-out), we are able to detect a 4 point difference of change in BDNF between intervention and control groups using two-sample t-test with 80% power (alpha=0.05). This calculation assumes a conservative estimate of SD of change in the above calculation (SD=6.4, the largest SD of outcome in the above study).

9.2. Define plans for data and statistical analysis, including key elements of the statistical plan, stopping rules and endpoints.

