Aim 1: The primary outcome of this aim is comparison of the change in average UPDRS motor scores between the exercise and no intervention groups after 8 weeks. Between groups changes will be assessed with a two (independent) sample t-test. Secondarily, within group changes from baseline for UPDRS scores and quantitative assessments will be assessed using paired t-tests. Additionally, the relationship between change in fitness (Vo2max) and change in UPDRS scores will be assessed using partial correlations controlling for age, gender and baseline fitness levels. An intention-to-treat analysis will be applied primarily but pre-planned secondary analyses will compare only exercise subjects deemed compliant with controls.

Aim 2: The primary outcome of this aim is comparison of the change in semi-quantitative DaT uptake from scans at baseline and 52 weeks (post-intervention). Because DaT SPECT signal loss is most sensitively detected in the putamen (particularly posterior putamen) in early PD(69), we will focus the primary analysis on this region, though we will also examine signal changes in the caudate, anterior putamen and an index of right/left asymmetry. Differences in the rate of DaT signal change between groups will also be assessed using linear mixed-effects models which will allow us control for the influence of age, gender or other confounders. Linear mixed-effects modelling also accommodates the inclusion of data points with different follow-up times, allowing the analysis to include all subjects even if they do not complete the full intervention period. In this analysis, we will determine whether there is a significant effect of the “treatment group x time” interaction (rate of change) on the predictive value of models with DaT uptake as the dependent variable. An intention-to-treat analysis will be applied primarily but pre-planned secondary analyses will compare only exercise subjects deemed compliant with controls.

Aim 3: The primary outcome of this aim will be differences in the rate of change between intervention groups as assessed using independent samples t-tests. A secondary outcome will examine the rate of change using linear mixed-effects models controlling for age, gender and other potential confounders. Additionally, relationships of biomarkers to VO2max, UPDRS, quantitative motor and quantitative DaT will be examined using partial correlations controlling for age and gender.

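### Aim 3 gives primary status to t-tests on three serum markers at two follow-up visits without naming a deciding marker, a time window or any multiplicity control

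*Combined protocol and SAP*

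**What the plan says.** The Aim 3 text in section 5.1.1 states the hypothesis for the markers as a group: "we will test the hypothesis that serum biomarkers of exercise effects and PD risk will change in the intervention group compared to no intervention". It then lists them: "Serum biomarkers associated with PD risk or exercise-induced changes (i.e. BDNF, uric acid and apolipoproteinA1) will be measured at baseline, 8 and 52 weeks". The primary outcome appears in the same words in sections 5.1.1 and 9.2: "The primary outcome of this aim will be differences in the rate of change between intervention groups as assessed using independent samples t-tests". Neither place says which marker decides the aim, which interval the rate of change covers, in what order the tests are read, or how alpha is shared. Section 9.2 gives no alpha for Aim 3.

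The only Aim 3 alpha is in the power paragraph of section 9.1, which deals with BDNF alone: "we are able to detect a 4 point difference of change in BDNF between intervention and control groups using two-sample t-test with 80% power (alpha=0.05"). That paragraph does not call BDNF the primary marker. Uric acid and apolipoprotein A1 have no power statement.

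The other two aims are tighter. In section 9.2, Aim 1 names one variable (UPDRS motor score) at 8 weeks. Aim 2 names one imaging measure from baseline to 52 weeks and focuses its primary analysis on the putamen.

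**The concern.** Where a primary outcome spans several variables and no rule says which one counts, the choice can be made after the data are seen. A chance difference in uric acid or apolipoprotein A1 could then be reported as a positive primary result for the aim even if BDNF, the only marker the trial was sized on, shows nothing. The background in section 3.1 gives BDNF a specific rationale. It says that the other two have not been studied directly in this role and only may respond to exercise. Leaving the window open adds to the problem, because an early and a late comparison are both available for each marker.

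**Working it through.** **Inputs from the documents**
- Markers: 3. Follow-up visits: 2 (weeks 8 and 52). Section 5.1.1, Aim 3.
- Alpha 0.05, BDNF difference 4 points, SD of change 6.4, 35 completers per group. Section 9.1, Aim 3.

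**Assumptions, because the documents are silent**
- Tests are two-sided.
- Each marker is tested at 0.05.
- Significance on any one marker is read as support for the aim.
- Correlations between test statistics range from 0 to 0.9.

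**Step 1. The plan's own figure.** The standard error is 6.4 × √(2/35) = 1.530, and 4/1.530 = 2.615. Power is Φ(2.615 − 1.960) = 74.4%, or 73.2% with the t distribution. The stated 80% is therefore not reproduced: it needs 41–42 per group, and the difference detectable with 35 per group is 4.35. A one-sided 0.05 test gives 83.4%, which does not match either. This is a separate matter, but it shows that BDNF has no power to spare.

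**Step 2. Three markers, one window.** Under independence, 1 − 0.95³ = 14.3%. With equally correlated test statistics:

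| Correlation | Chance of at least one false positive |
|---|---|
| 0 | 14.3% |
| 0.5 | 12.5% |
| 0.8 | 9.8% |
| 0.9 | 8.4% |

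Simulated t-tests at 35 per group agree: 12.6% at 0.5 and 8.4% at 0.9.

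**Step 3. Three markers, both windows.** Under independence, 1 − 0.95⁶ = 26.5%. With marker correlations of 0 to 0.5 and between-window correlations of 0.3 to 0.7, simulation gives about 20% to 26%. With a single common correlation of 0.8 it is 13.9%.

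**Step 4. Would naming BDNF alone be enough?** Not if it is tested at both visits: 1 − 0.95² = 9.75% under independence and 9.1% at correlation 0.5. The window has to be named as well.

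**Step 5. The alternative of splitting alpha.** At 0.05/3 = 0.0167 per marker the critical value is 2.394. BDNF power at 35 per group falls to Φ(2.615 − 2.394) = 58.7%, or 56.6% with the t distribution. Restoring 80% would take 54–56 per group.

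**The case against.** The strongest reply is that the plan states no success rule. A reader might infer that the Aim 3 error rate simply is 12–14%, or 2.5 to 2.9 times the stated alpha. The documents do not support that. It requires both that any one marker suffices and that each is tested at 0.05, and section 9.2 says neither. If each marker is reported on its own terms, each test carries 5%. The 12–14% range also covers only low to moderate correlation, and the documents give no correlation. This part of the reply stands, so the figures have to be conditional and shown over the full range.

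A second reply is that Aim 3 is mechanistic. Section 4 speaks of characterizing correlates and of relationships that will suggest pathways, which is softer than confirmatory language. That lowers the importance of the point but does not remove it, because sections 5.1.1 and 9.2 still declare a hypothesis to be tested and a primary outcome.

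A third reply is that sizing on BDNF shows it was the intended primary marker. That is plausible, and the BDNF test at a single window would then carry 5%. But no section says so, and the hypothesis also covers markers of PD risk, so the inference is not secure.

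Finally, the six-test figure is conditional. A rate of change could mean one slope per subject over all visits, in which case there are three tests, not six.

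**Conclusion.** The gap is real: a declared primary outcome covers three markers and two follow-up visits, with no deciding marker, window or multiplicity rule. Its effect on the error rate is conditional. If any one marker is allowed to carry the aim and each is tested at two-sided 0.05, the chance of at least one false positive when exercise affects none of them lies between about 8% and 14% for one window, depending on a correlation that the documents do not give. The upper limit is 26.5% if both visits are tested and all tests are independent. Throughout the range shown it exceeds 5%. Because the aim is mechanistic and Aims 1 and 2 are untouched, this is a cheap improvement and not a threat to the trial's main conclusions.

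**What to change.** In section 9.2, and in the matching Aim 3 text of section 5.1.1, name change in BDNF over one stated window as the single Aim 3 primary outcome, tested two-sided at 0.05. Baseline to 8 weeks is one candidate, since section 9.1 describes the BDNF study used for sizing as an 8-week intervention. Section 3.1, citing the same reference, describes 4 weeks, so the sponsor should reconcile the two before relying on that argument. Label uric acid, apolipoprotein A1 and the other window either as secondary, with Holm adjustment, or as exploratory, reported as estimates with confidence intervals.

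The cost is wording only: no extra data or participants, and BDNF keeps its full alpha. The downside is that uric acid or apolipoprotein A1, the PD-risk markers, can no longer carry the aim alone. If the sponsor wants them to, all three can be tested with Holm over one named window, at the price of lower BDNF power; the equal split in step 5 of the working shows the size of that loss.

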9.1. Include statistical power calculations and the assumptions made in making these

calculations.

Aim 1: A meta-analysis of 39 physiotherapy and exercise intervention trials in PD estimated an effect size (mean(SD)) of a 5.0(7.3) point improvement in UPDRS motor score comparing intervention to control groups (6). This change in UPDRS motor score corresponds to a “moderate clinically meaningful difference” as described by Shulman and colleagues(100). Using a two-sample t-test with 80% power, we need 35 subjects per group to detect this difference between the control and intervention groups. Accounting for 20% drop-out, we would need 44 subjects per group. Recent studies completed by [name] and EMU staff include 2 community-based weightlifting interventions lasting 52-weeks with drop-out rates of 8% (N=141 randomized) and 14% (N=154 randomized)(101, 102). A two-year trial with a similar intervention had a drop-out rate of 13% (N=164 randomized) (103). EMU staff and protocols have been very successful in promoting retention in long-term exercise trials. The drop-out rate assumed for this aim may be an over-estimate for the short-term intervention but allows recruitment to adequately power the long-term intervention in Aim 2, as well. Based on our preliminary data that approximately 50% of DIP subjects have olfactory deficits and that hyposmia is strongly predictive of abnormal DaT (we will assume 75% of subjects with hyposmia will have DaT SPECT abnormalities), we anticipate screening approximately 250 DIP subjects with olfactory tests to achieve the required cohort size. Olfactory screening with the UPSIT is straightforward and can be completed in 15-20 minutes.

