9.3. Provide sample size determination and analysis (include anticipated rate of screen failures, study discontinuations, lost to follow-up, etc.)

Based on power calculations, we anticipate screening 250 DIP subjects with olfactory testing, with the expectation that approximately 125 (50% of those screened) will be included in the imaging cohort, 88 (75% of those with abnormal olfactory testing) will be enrolled in exercise cohort and approximately 70 (assuming a 20% drop-out rate) will complete the study. 2018 Amendment: We anticipate enrolling 56 additional subjects under the modified inclusion criteria with 48 (24 per group) expected to complete all study activities. This will still allow for meaningful analysis of our primary outcomes according to the sensitivity analysis of sample size from the original protocol (20 per group adequate).

9.4. Describe how, where and by whom the data will be analyzed.

Preliminary statistical analyses will be conducted by the PI in the CMC PADRECC. Coded data will also be analyzed by [name], Associate Professor of Biostatistics at Penn and statistical advisor on [name] CDA award. [name] will have no access to the code that relates subjects' PHI to their study data

Section 10: References - Bibliography of cited literature

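### The 2018 amendment calls 20 per group adequate for the primary outcomes, but that figure belongs to Aim 2 alone; on the plan's own inputs Aim 1 has about 64% power at 24 per group

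*Combined protocol and SAP*

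**What the plan says.** Section 9.1 sizes each aim separately.

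- **Aim 1** (change in UPDRS motor score at 8 weeks) takes a 5.0-point difference with SD 7.3 and 80% power, giving 35 per group. Then: "Accounting for 20% drop-out, we would need 44 subjects per group".
- **Aim 2** (change in putamen DaT signal at 52 weeks) starts from the same completers: "With 35 subjects per group expected to complete the study (accounting for 20% drop-out"). The planned control decline is 0.15. A sensitivity series follows for faster decline: 29 per group if it is 10% faster, then "If the rate were 20% higher, we could detect a similar effect with 24 subjects", then 20 per group if the decline is 0.20.
- **Aim 3** (BDNF) takes a 4-point difference with SD 6.4 and again 35 per group.

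Section 9.2 names a primary outcome for each of the three aims.

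Section 9.3 carries the 20% drop-out through 88 randomized subjects, of whom "approximately 70 (assuming a 20% drop-out rate) will complete the study". The 2018 amendment follows directly: "We anticipate enrolling 56 additional subjects under the modified inclusion criteria with 48 (24 per group) expected to complete all study activities". Its next sentence says the primary outcomes, in the plural, can still be meaningfully analysed, and cites the sensitivity analysis as showing that 20 per group is enough. Section 5.1.3 repeats both sentences; 5.2.1 repeats only the numbers.

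**The concern.** The amendment takes a threshold derived for one endpoint under one favourable assumption and applies it to all the primary outcomes. The sensitivity series concerns only putamen signal. It says nothing about the UPDRS motor score or BDNF, whose effect sizes and SDs do not depend on how fast DaT signal declines.

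Even within Aim 2, 20 per group applies only at a control decline of 0.20. At the planned 0.15 the plan itself asks for 35. The reason section 9.1 gives for expecting a faster decline is that subjects are prodromal and not yet clinically manifest, yet the current inclusion criteria (5.1.1 and 5.4.5.1) also admit clinically diagnosed PD at Hoehn and Yahr stage 2 or below.

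At stake is how a null Aim 1 result would be read. Someone relying on 9.3 would think the trial had about its planned chance of detecting 5 points, when on the plan's inputs that chance is well below 80%. Separately, the amendment's completer count uses a drop-out rate that differs from the rest of the section and is not stated.

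**Working it through.** **Inputs.** All come from section 9.1 or 9.3: Aim 1 difference 5.0, SD 7.3; Aim 3 difference 4, SD 6.4; Aim 2 control decline 0.15 with 35 per group; 56 enrolled and 48 completing under the amendment; 1:1 allocation (5.1.1), so 28 enrolled per group. The test is the plan's two-sample t-test. Two-sided alpha 0.05 is my assumption, since sidedness is not stated.

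**1. Reproduce the plan's Aim 1 figure.** Standardised difference 5.0/7.3 = 0.685. The t-test needs 34.4, so 35 per group (power 80.6%). Then 35/0.80 = 43.75, so 44 per group, and 88 × 0.80 = 70.4. The original chain holds.

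**2. Trace the 20 per group.** The planned effect is 0.06/0.15 = 40% of the control decline. If that ratio and the SD are held fixed, n scales as 35 × (0.15/decline)²:
- decline 0.165: 28.9 (plan: 29)
- decline 0.18: 24.3 (plan: 24)
- decline 0.20: 19.7 (plan: 20)

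So the 20 is an Aim 2 number that needs a decline of 0.20 and, with it, a group difference of 0.40 × 0.20 = 0.08. I take the series at face value here. It reproduces with an SD of change of about 0.088, not the stated 0.13, which is a separate question.

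**3. Aims 1 and 3 at the amendment's numbers.** Power is from the noncentral t distribution. The detectable difference is SD × d(n), where d(n) is the standardised difference giving 80% power.

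| Per group | d(n) | Aim 1 power | Aim 1 detectable (7.3 × d) | Aim 3 power |
|---|---|---|---|---|
| 20 | 0.909 | 56% | 6.6 | 49% |
| 22 | 0.865 | 60% | 6.3 | 53% |
| 24 | 0.826 | 64% | 6.0 | 56% |
| 28 | 0.762 | 71% | 5.6 | 63% |
| 35 | 0.679 | 81% | 5.0 | 73% |

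The 28 row is the best case for Aim 1: nobody lost by week 8. Aim 3 is already below 80% at 35, because 4/6.4 = 0.625 needs 41.2, so 42 per group.

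**4. Drop-out.**
- Implied by the amendment: 1 − 48/56 = 14.3%.
- At the plan's 20%: 56 × 0.80 = 44.8 completers, 22.4 per group. Having 24 per group complete would need 48/0.80 = 60 enrolled.
- At the 14% and 13% reported for earlier trials in 9.1: 56 × 0.86 = 48.2 and 56 × 0.87 = 48.7.
- Completers stay at or above 20 per group until drop-out reaches 1 − 40/56 = 28.6%.

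**The case against.** A reader who notices the change of drop-out rate might infer that the amendment contains an arithmetic error and cannot deliver 24 per group, or that at 22 per group its support in the sensitivity series disappears. The documents do not support either reading.

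Section 9.1 reports drop-out in the same exercise unit's trials: "2 community-based weightlifting interventions lasting 52-weeks with drop-out rates of 8% (N=141 randomized) and 14% (N=154 randomized"), and "A two-year trial with a similar intervention had a drop-out rate of 13% (N=164 randomized"). A rate of 14% gives the stated 48. Those trials tested weightlifting or strength training, the amendment does not cite them, and the plan had them in hand when it chose 20%: "The drop-out rate assumed for this aim may be an over-estimate for the short-term intervention but allows recruitment to adequately power the long-term intervention". That makes the change an unlabelled assumption. Nor does the amendment lean on the 24-per-group row; its only threshold is 20, which 22 per group still meets. Moving from 24 to 22 costs about 4 points of Aim 1 power.

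Three further objections bear on the Aim 1 figures.

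- **Timing.** Aim 1 is read at week 8, while 24 counts those finishing all activities to week 52. This stands, which is why the 28-per-group row is shown; power there is still 71%.
- **Pooling.** The 56 are additional subjects, and those randomized before 2018 may be pooled with them. This also stands. The documents give neither their number nor the intention, so the powers above are conditional.
- **Analysis set.** For Aim 2 the mixed model uses subjects with shorter follow-up, and a final scan is sought from those leaving after 24 weeks. Completer counts are therefore not the whole analysis set there, but this does nothing for Aim 1.

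**Conclusion.** The adequacy statement is wrong as written. Twenty per group is a conditional Aim 2 figure and does not carry over to the other primary outcomes. On the plan's own inputs Aim 1 has 56% to 64% power at 20 to 24 per group and at most 71% with 28. The difference detectable with 80% power is 5.6 to 6.6 points, against the planned 5.0. Aim 3 has about 53% to 56% at 22 to 24.

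This rests on a two-sided alpha of 0.05, the plan's SDs, and analysis of the 56 alone; pooling with earlier subjects would raise the power by an amount the documents do not allow one to compute. The conclusion about Aim 1 holds under either drop-out rate, because most of the fall from 81% comes from the smaller target and little from 14% versus 20%. On its own the drop-out discrepancy is a minor clarification.

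**What to change.** In 9.3 and 5.1.3, replace the general adequacy sentence with the power or detectable difference for each aim at the number expected at its own time point: week 8 for Aim 1, week 52 for Aim 2, and the stated biomarker time point for Aim 3. Say that 20 per group refers to Aim 2 only, and only if the control decline is 0.20. State whether subjects enrolled before 2018 are pooled with the 56 and, if so, how many there are.

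In 9.3, 5.1.3 and 5.2.1, either give the roughly 14% drop-out rate with its source in the unit's earlier trials, or keep 20% and report about 22 completers per group.

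The cost is revised text in three sections. No extra patients are needed, though the stated figures become less favourable.

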Patients aged 40-89 with a clinical diagnosis of DIP will be recruited from the CMC VAMC PADRECC and Behavioral Health Service (BHS) clinics. We will recruit subjects with parkinsonian signs (rest tremor, rigidity, bradykinesia) occurring after the institution of therapy with a antipsychotic medication having known dopamine receptor blocking activity (examples include haloperidol, chlorpromazine, fluphenazine, perphenazine, risperidone, thioridazine, thiothixene, ziprasidone, olanzapine and aripiprazole). Potential subjects with DIP will be pre-screened using a brief (12 item) scratch and sniff smell test with hyposmic subjects invited to learn more about the study (see script). Brief olfactory testing should be completed in 5-10 minutes. We anticipate screening 250 subjects with olfactory testing. Approximately 120 subjects will undergo baseline assessment including DaT-SPECT as described above. Subjects with abnormal DaT-SPECT will be invited to be randomized into the exercise study. In addition to the screening described above, we will invite subjects from [name] CPPF pilot study "Degenerative nigrostriatal dysfunction in drug-induced parkinsonism" PROM#01481 who have abnormal DaT-SPECT to enroll in the present protocol. These subjects will have explicitly agreed to future contact for related studies in the ICF for PROM#01481. We may also invite subjects identified by their PADRECC provider who had DaT-SPECT (with an abnormal result) performed clinically outside of a research protocol within the prior 3 months and agree to be contacted. We will randomize 88 subjects to either exercise intervention or no intervention and anticipate that 70 subjects will complete all aspects of the study. Additionally, letters will be sent to potential participants letting them know that they may be eligible for a study with a brief description of the study and give them a number of they would like to learn more or to request no further contact. 2018 Amendment: We anticipate enrolling 56 additional subjects under the modified inclusion criteria with 48 (24 per group) expected to complete all study activities. This will still allow for meaningful analysis of our primary outcomes according to the sensitivity analysis of sample size from the original protocol (20 per group adequate).

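### The 2018 amendment calls 24 completers per group enough for the primary outcomes by citing a figure of 20 that applies only to Aim 2 at a faster decline; Aim 1 needs 35 by the plan's own calculation

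*Combined protocol and SAP*

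**What the plan says.** Sections 5.1.3 and 9.3 give the amended size: "We anticipate enrolling 56 additional subjects under the modified inclusion criteria with 48 (24 per group) expected to complete all study activities". Both then justify it in the same words, as permitting "analysis of our primary outcomes according to the sensitivity analysis of sample size from the original protocol (20 per group adequate").

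Section 9.2 defines a separate primary outcome for each aim: change in UPDRS motor score at 8 weeks (Aim 1), change in putamen DaT uptake at 52 weeks (Aim 2), and change in serum biomarkers (Aim 3).

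Section 9.1 sizes each aim:

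- **Aim 1** (5.0 points, SD 7.3): "Using a two-sample t-test with 80% power, we need 35 subjects per group to detect this difference". No sensitivity analysis is given.
- **Aim 2** (declines of 0.15 and 0.09): 35 per group in the base case, followed by the only sensitivity analysis in the plan. The case that matches the amended size reads "If the rate were 20% higher, we could detect a similar effect with 24 subjects". The case that yields 20 reads "If the baseline rate of decline were 0.2 rather than 0.15 (33% higher), we could detect the effect with only 20 subjects per group". The reason offered for a faster decline is this: "striatal degeneration during the prodromal period that we will capture may be greater than what been reported for the clinically manifest period of PD".
- **Aim 3** (4 points, SD 6.4): 35 per group. No sensitivity analysis is given.

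**The concern.** The amendment takes the most favourable case of one aim's sensitivity analysis and uses it to cover all primary outcomes. Four things do not fit.

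1. The figure of 20 belongs to Aim 2 only and depends on a decline one third faster than assumed. Even the case giving 24 needs a decline of 0.18.
2. For Aim 1 the plan's own requirement is 35, so 20 or 24 contradicts it directly.
3. The reason for expecting faster decline concerns prodromal disease, as opposed to clinically manifest PD. Sections 5.1.1 and 5.4.5.1 now admit patients with clinically diagnosed PD up to Hoehn & Yahr stage 2, to whom that reason does not apply. That the amendment added them is inferred from its reference to modified inclusion criteria. DIP subjects remain eligible and the mix is not given.
4. The 56 subjects are additional, but the number of earlier completers is not stated, so the final sample size and its power cannot be read from the plan.

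A reader would conclude that every primary outcome remains adequately sized. A null result on Aim 1 or Aim 3 could then be given more weight than the sample supports.

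**Working it through.** **Method.** Two-sample t-test, n per group, two-sided alpha 0.05. Alpha is stated for Aims 2 and 3 and assumed for Aim 1. Power is P(|T| > t crit) for a noncentral t with 2n − 2 degrees of freedom and noncentrality (Δ/SD) × √(n/2).

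**Reproducing Aim 1.** Δ/SD = 5.0/7.3 = 0.685. The n for 80% power is 34.4, so 35 per group, as the plan states. With 20% drop-out, 35/0.8 = 43.75, so 44, also as stated. One-sided testing would give 27, so the plan's 35 is two-sided.

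**Reproducing the Aim 2 series.** The SD that gives 80% power for 0.06 at n = 35 is 0.0883. Two readings of a similar effect were tried with that SD:

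| Control decline | Plan's n | n, constant 40% slowing (Δ) | n, intervention decline fixed at 0.09 |
|---|---|---|---|
| 0.15 | 35 | 35.0 (0.060) | 35.0 |
| 0.165 | 29 | 29.1 (0.066) | 22.8 |
| 0.18 | 24 | 24.6 (0.072) | 16.1 |
| 0.20 | 20 | 20.1 (0.080) | 11.2 |

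Constant 40% slowing matches the plan; the fixed-decline reading does not. So the 20 is an Aim 2 figure for Δ = 0.08 at a decline of 0.20.

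**Aim 1 sample at 8 weeks.** The amendment randomizes 56/2 = 28 per group and expects 24 to complete everything (drop-out 1 − 48/56 = 14.3%). Aim 1 is read at 8 weeks, and Section 9.1 says of its 20% allowance: "The drop-out rate assumed for this aim may be an over-estimate for the short-term intervention". So 28 is the upper bound for Aim 1.

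**Power if amendment subjects are analysed alone, base-case inputs.**

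| Outcome | n = 24 | n = 28 | n = 35 |
|---|---|---|---|
| Aim 1: 5.0 points, SD 7.3 | 64.2% | 71.1% | 80.6% |
| Aim 2: 0.06, implied SD 0.0883 | 63.5% | – | 80.0% |
| Aim 3: 4 points, SD 6.4 | 56.3% | – | 73.2% |

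At the 20 per group called adequate, Aim 1 power is 56.0%.

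**Detectable difference at 80% power.** Aim 1: 6.0 points at 24 and 5.6 at 28. Aim 2 at 24, implied SD: 0.073, which is 0.073/0.15 = 49% slowing.

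**Aim 2 under faster decline, n = 24, implied SD, 40% slowing.** 79% at a decline of 0.18 and 87% at 0.20.

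**Separate matter.** Section 9.1 states an SD of change of 0.13, not 0.088. With 0.13, base-case Aim 2 power is 35% at 24 but already 48% at 35. At a decline of 0.20 and n = 24 it is 55% for 40% slowing (82% if the intervention group declines by 0.09). That discrepancy, and the 73% for Aim 3 at 35, belong to the original calculation; the amendment did not cause them.

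**Earlier completers needed to reach 35 for Aim 1.** 35 − 24 = 11 per group, or 35 − 28 = 7 per group if all randomized subjects give 8-week data.

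**The case against.** The strongest reply is that the 56 are additional subjects and the plan nowhere says they will be analysed apart. Pooling with those already randomized is a natural reading, and a modest number of earlier completers would restore Aim 1. This stands as a limit on the consequence: the documents do not show that Aim 1 will be underpowered. It does not rescue the justification, which argues from 24 against 20 and relies on no pooled total.

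A second reply is that the amendment claims only a meaningful analysis, not 80% power. But it rests that claim on a power-based sensitivity analysis and calls a specific number adequate, so it is a sample-size claim.

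Third, the citation is legitimate for Aim 2 if qualified, since 24 per group gives close to 80% power or more at declines of 0.18 and 0.20 with the implied SD. That is fair, and it supports keeping those scenarios under Aim 2 with their assumption named. It gives no support for Aims 1 and 3.

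Finally, the effect of admitting clinically diagnosed PD cannot be quantified, because the mix is unknown and the faster prodromal decline is offered only as a possibility. That point is context; the main contradiction does not depend on it.

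**Conclusion.** The concern holds. The adequacy statement in Sections 5.1.3 and 9.3 is not supported by its source: it carries one favourable Aim 2 scenario over to all primary outcomes and conflicts with the 35 per group required for Aim 1. On the only sample size the amendment gives, power falls about 10 to 16 percentage points below the original for Aim 1 (80.6 − 71.1 = 9.5; 80.6 − 64.2 = 16.4), by 80.0 − 63.5 = 16.5 points for base-case Aim 2, and by 73.2 − 56.3 = 16.9 points for Aim 3.

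These sizes assume that amendment subjects are analysed alone, two-sided alpha of 0.05 for Aim 1, and the implied SD of 0.0883 for Aim 2. With pooling the losses shrink by an amount the plan does not allow one to calculate. The misattribution itself needs none of these assumptions. It must be corrected, because it is the only justification given for the amended sample size.

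**What to change.** In Sections 5.1.3 and 9.3, remove the statement that 20 per group is adequate and its reference to the sensitivity analysis. In its place:

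1. State the expected total completers per group, earlier plus amendment subjects, and whether the two cohorts are pooled.
2. At that n, give power or detectable difference for each primary outcome under base-case inputs: Aim 1, 5.0 points with SD 7.3; Aim 2, 0.06 at a decline of 0.15, naming the SD of change used; Aim 3, 4 points with SD 6.4. For Aim 1, also give the number expected at 8 weeks.
3. If amendment subjects are to be analysed alone, enter Aim 1 as 64% at 24 per group (71% at 28), detectable difference 6.0 points (5.6 at 28).
4. Label any faster-decline scenario as applying to Aim 2 in prodromal subjects only, with the decline assumed.

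The cost is rewording two sections and supplying the count of earlier completers. No patients, visits or analyses are added. The drawback is that the stated power will look less favourable.
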